8.3.7 REPORTING EVENTS TO PARTICIPANTS

Participants will be notified at an aggregate level about any AEs or SAEs affecting >5% of the study population.

8.3.8 EVENTS OF SPECIAL INTEREST

There are no additional events of special interest beyond those that have already been described.

8.3.9 REPORTING OF PREGNANCY

As patients are being admitted to the study with early pregnancy loss, no new pregnancies will be assessed during the study period.

8.4 UNANTICIPATED PROBLEMS

8.4.1 DEFINITION OF UNANTICIPATED PROBLEMS (UP)

The Office for Human Research Protections (OHRP) considers unanticipated problems involving risks to participants or others to include, in general, any incident, experience, or outcome that meets all of the following criteria:

- Unexpected in terms of nature, severity, or frequency given (a) the research procedures that are
 described in the protocol-related documents, such as the Institutional Review Board (IRB)approved research protocol and informed consent document; and (b) the characteristics of the
 participant population being studied;
- Related or possibly related to participation in the research ("possibly related" means there is a
 reasonable possibility that the incident, experience, or outcome may have been caused by the
 procedures involved in the research); and
- Suggests that the research places participants or others at a greater risk of harm (including physical, psychological, economic, or social harm) than was previously known or recognized.

8.4.2 UNANTICIPATED PROBLEM REPORTING

Research personnel will report unanticipated problems (UPs) to the reviewing Institutional Review Board (IRB) and to the principal investigator (PI). The UP report will include the following information:

- Protocol identifying information: protocol title and number, PI's name, and the IRB project number;
- A detailed description of the event, incident, experience, or outcome;
- An explanation of the basis for determining that the event, incident, experience, or outcome represents an UP;
- A description of any changes to the protocol or other corrective actions that have been taken or are proposed in response to the UP.

To satisfy the requirement for prompt reporting, UPs will be reported using the following timeline:

- UPs that are serious adverse events (SAEs) will be reported to the IRB and to the study sponsor within 7 days of the investigator becoming aware of the event.
- Any other UP will be reported to the IRB and to the study sponsor within 30 days of the investigator becoming aware of the problem.

All UPs should be reported to appropriate institutional officials (as required by an institution's
written reporting procedures), the supporting agency head (or designee), and the Office for
Human Research Protections (OHRP) within 7 days of the IRB's receipt of the report of the
problem from the investigator.

8.4.3 REPORTING UNANTICIPATED PROBLEMS TO PARTICIPANTS Not applicable.

9 STATISTICAL CONSIDERATIONS

9.1 RESEARCH HYPOTHESES

- Primary Outcome Variable(s):
 - o Feasibility:
 - Recruitment: >60% participants screened for participation enrolled in study
 - Adherence: >50% participants took study medications at the appropriate time and route
 - Retention: >90% participants had complete follow up for all study visits
- Secondary Outcome Variable(s): This is a pilot study with a small sample size and thus our secondary aims will only be for hypothesis generating activities, not hypothesis testing activities.

9.2 SAMPLE SIZE RATIONALE

As this is a feasibility pilot study, no formal power calculation is required. We anticipate recruiting a convenience sample of 40 participants over the course of 12 months recruitment based on prior information from UNC Chapel Hill where approximately two patients with EPL are diagnosed per week at our two study locations after accounting for eligibility criteria and desire participation in the study. We estimate that of the approximately 100 patients diagnosed with EPL over the year, 40 patients will enroll given prior recruitment rates from studying mifepristone and misoprostol for early pregnancy loss (800 EPL patients for a total of 300 participants) [2].

9.3 POPULATIONS FOR ANALYSES

As no randomization will take place in this analysis, all participants will be analyzed as part of the same population using univariate statistics. For the primary endpoint of feasibility, all patients screened for study participation will be included in the sample size. For the secondary endpoints of resolution of EPL, side effects/adverse events and patient acceptability, only participants adherent to study medication and completing all study visits will be analyzed. A sensitivity analysis will be conducted for the secondary endpoints that will include all participants enrolled in the study population for which data is available, regardless of adherence to study medication or completion of all study visits.

Patient disposition in the study will be reported, including the following:

- Number (%) of patients screened for study participation
- Number (%) of patients enrolled in study population
- Number (%) of participants adherent to study medication (UPA + misoprostol after 6 to 18 hours)
- Number (%) of participants non-adherent to study medication (any other route or timing of taking study medications)
- Number (%) of participants completing all study visits (day 0, day 3/8, day 30)

• Number (%) of participants completing some of study visits

Patient disposition will be reported as a flow chart and in tabular format in any future study communication and manuscript.

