- Participant is screened for eligibility by the study coordinator and offered admission to study if eligible
 - Review of radiologic imaging to confirm early pregnancy loss based on eligibility criteria
 - Review of physical exam findings and vital signs (heart rate, blood pressure, temperature) to ensure that patient is hemodynamically stable and not having an inevitable or incomplete abortion based on eligibility criteria
- Participant reviews and signs informed consent and HIPAA authorization form
- Participant completes paper baseline demographic questionnaire
- Participant will have hemoglobin, ABO/Rh status and liver function testing (ALT, AST, total bilirubin) if not already performed by primary OBGYN

 Participant takes 90mg ulipristal acetate with study team; given prescription for 800mcg misoprostol to take at home

Visit 2 (Day 3 ± 1 day):

- Participant returns to UNC Family Planning Clinic
- Participant has vital signs checked by RN at clinic
- Participant fills out questionnaire regarding bleeding symptoms and any side effects or adverse
 events after taking the ulipristal acetate and misoprostol, including reporting time and route of
 administration of misoprostol at home
- Participant has a transvaginal ultrasound completed by the principal investigator to ensure that the pregnancy has passed (no gestational sac visualized on ultrasound)
- If pregnancy is still in the uterus, patient will be offered surgical management, medical management (an additional dose of misoprostol 800mcg), or expectant management

Visit 3 (Day $8 \pm 1 \text{ day}$):

- Participant will only attend this visit if a gestational sac was still present on ultrasound on Visit
 2 and patient opted for medical management or expectant management. If gestational sac is absent at Visit 2, participant will not need Visit 3. All participants will complete Visit 4.
- Participant returns to UNC Family Planning Clinic
- Participant has vital signs checked by RN at clinic
- Participant fills out questionnaire regarding bleeding symptoms and any side effects or adverse events after taking the ulipristal acetate and misoprostol
- Participant has transvaginal ultrasound completed by the principal investigator to ensure that the pregnancy has passed (no gestational sac visualized on ultrasound)
- If pregnancy is still in the uterus, patient will be offered surgical management, medical management (if patient did not receive additional misoprostol at Visit 2), or expectant management

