6.4 STUDY INTERVENTION COMPLIANCE

Patients will take UPA in the presence of study staff prior to discharge from visit 1. Participants will report the time that they self-administered misoprostol vaginally on their return for their day 3 transvaginal ultrasound.

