7.2 PARTICIPANT DISCONTINUATION/WITHDRAWAL FROM THE STUDY

Participants are free to withdraw from participation in the study at any time upon request. An investigator may discontinue or withdraw a participant from the study for the following reasons:

Significant study intervention non-compliance

- If any clinical adverse event (AE), laboratory abnormality, or other medical condition or situation occurs such that continued participation in the study would not be in the best interest of the participant
- If the participant meets an exclusion criterion (either newly developed or not previously recognized) that precludes further study participation
- Participant presents for enrollment >2 weeks following diagnosis of early pregnancy loss as over 50% of participants will have complete miscarriage with expectant management alone at this time point [27].

The reason for participant discontinuation or withdrawal from the study will be recorded on the Case Report Form (CRF). Subjects who sign the informed consent form but do not receive the study intervention may be replaced.

Participants who discontinue or withdraw from the study will not be replaced. Instead, additional enrollment will commence to reach the targeted sample size of 40 study participants.

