8.3.5 ADVERSE EVENT REPORTING

Adverse event reporting by patient self-report will take place at each study visit, both in person and via telephone. Additionally, any adverse event that happens between study visits for which the participant seeks care at UNC Chapel Hill will be abstracted from the UNC EPIC electronic medical record. All adverse events will be recorded on case report forms (CRF) and will be reviewed by the principal investigator and mentor. Case report forms should be documented within 24 hours of the event, and review of the case report forms will occur on a weekly basis.

Likely mild medication side effects as detailed for UPA include headache (18%), nausea (12%), abdominal pain (12%). Other infrequent mild side effects include dysmenorrhea, fatigue and dizziness [14]. All patients may experience pain and discomfort during the process of pregnancy expulsion; however, this pain and discomfort are not different than what a patient would experience not in the study. Assessment of adverse events will include symptoms possibly related to the study medication and pregnancy expulsion, but will also include any additional adverse events experienced by the study participants.

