9.4 STATISTICAL ANALYSES

9.4.1 GENERAL APPROACH

Continuous variables will be summarized using mean and standard deviation or median and range depending on the distribution and categorical variables will be described as frequency and percentage. All statistics will be reported with 95% confidence intervals. Where applicable, missing data will be reported as an individual category. As this is a pilot feasibility study with a small sample size, no formal statistical testing will be completed. The principal investigator will be responsible for all data management and data analysis. Statistical calculations will be performed in Stata 15.1.

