9.4.4 SAFETY ANALYSES

AEs will be reported by frequency and percentage of participants presenting with the outcomes. Specific side effects and adverse events of interest are listed with secondary outcomes (9.4.3). All other side effects and adverse events outside of those listed in 9.4.3 will also be reported by frequency and percentage. Other AEs will be reported by severity of the adverse events (mild, moderate or severe) and related or not related to the study protocol. AEs will be grouped by Medical Dictionary for Regulatory Activity (MedDRA) System Organ Class (SOC).

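### Section 9.3 makes adherent completers the lead set for side effects, adverse events and resolution, a set fixed only after UPA intake, and 9.4.4 names no other denominator

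*Combined protocol and SAP*

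**What the plan says.** Section 9.3 (Populations for Analyses) takes resolution of early pregnancy loss, side effects/AEs and acceptability together and states that "only participants adherent to study medication and completing all study visits will be analyzed". It then adds: "A sensitivity analysis will be conducted for the secondary endpoints that will include all participants enrolled in the study population for which data is available", whether or not the woman adhered or completed every visit. The same section opens by saying that everyone will be analysed as a single population, which does not sit easily with this restriction.

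Five other sections bear on the point.

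- **Exposure.** Section 6.4: "Patients will take UPA in the presence of study staff prior to discharge from visit 1".
- **Adherence and completion.** Under 9.4.2, adherence means UPA followed by vaginal misoprostol at 6 to 18 hours. Retention means attending Day 0, Day 3/8 and Day 30.
- **Withdrawal.** Section 7.2 allows the investigator to withdraw a participant "If any clinical adverse event (AE), laboratory abnormality, or other medical condition or situation occurs such that continued participation in the study" is no longer in her interest.
- **Visit 3.** Section 4.1: "If gestational sac is absent at Visit 2, participant will not need Visit 3". The visit is for women with a sac still present on Day 3 who choose medical or expectant management.
- **AE capture and reporting.** Section 8.3.5: "any adverse event that happens between study visits for which the participant seeks care at UNC Chapel Hill will be abstracted" from the medical record. Section 9.4.4: "All other side effects and adverse events outside of those listed in 9.4.3 will also be reported by frequency and percentage", with no analysis set or denominator named.

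No set consisting of all women who received UPA is defined anywhere.

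**The concern.** An AE rate should have as its denominator the women exposed to the drug. Here exposure is known for every woman dosed, because staff watch her take UPA. The lead set is then narrowed by events that come later: when and by what route she took misoprostol at home, and whether she kept every contact up to the Day 30 call. A woman with a recorded AE can be absent from the lead AE rate. Because 9.4.4 is silent, the only set that the plan assigns to AEs is the restricted one. It is also unclear whether AEs outside the 9.4.3 list, such as a Day 14 liver-enzyme rise, are restricted in the same way.

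Two parts of the selection may also depend on the outcome.

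- A woman withdrawn for an AE who then misses her remaining visits leaves the lead set.
- If a required Day 8 visit counts toward the Day 3/8 item, only women who had not resolved by Day 3 have that extra visit to miss. One who misses it leaves the lead resolution rate although her Day 3 scan is known.

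This is the first study of UPA for this indication and is meant to inform a larger trial. Its estimates and safety counts are what that trial would carry forward.

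**Working it through.** **The plan's own figure.** The plan gives no size for the lead set and no precision target, so the only figure to reproduce is N = 40 (9.2). About 100 patients at the cited ratio of 300/800 gives 100 × 0.375 = 37.5. Two a week for 52 weeks gives 104 × 0.375 = 39. Both are close to 40. Below I assume 40 women dosed, each with AE information.

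**Size of the lead set.** Section 9.1 sets adherence above 50%, so at least 21 of 40, and retention above 90%, so at least 37 of 40. With A adherent and R retained, the overlap lies between A + R − 40 and min(A, R). The second and third rows are assumed values.

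| Adherent, retained | Lead set | Exact 95% upper limit if no events |
|---|---|---|
| 21, 37 (thresholds just met) | 18–21 | 18.5%–16.1% |
| 32, 38 | 30–32 | 11.6%–10.9% |
| 36, 38 | 34–36 | 10.3%–9.7% |
| All 40 dosed | 40 | 8.8% |

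The limit is two-sided Clopper-Pearson with zero events, 1 − 0.025^(1/n). For n = 18 this is 18.5%, for n = 21 it is 16.1%, and for n = 40 it is 8.8%. In the first row, 19 to 22 of the 40 exposed women are outside the lead analysis.

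**Effect on an observed AE rate.** Suppose 2 of 40 women have a given AE, which is 5.0%. A lead set of 30 shows 0/30 = 0%, 1/30 = 3.3% or 2/30 = 6.7%, according to how many of the two are in it. The lead rate can be lower or higher than the rate in all exposed women.

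**The Day 8 route alone.** Assume that a required Day 8 visit counts, that everyone adheres and that no other visit is missed. With S women resolved on Day 3 and k unresolved women missing Day 8, the lead rate is S/(40 − k). Retention above 90% of 40 allows k up to 3.

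| S | k = 0 | k = 1 | k = 2 | k = 3 |
|---|---|---|---|---|
| 32 | 80.0% | 82.1% | 84.2% | 86.5% |
| 28 | 70.0% | 71.8% | 73.7% | 75.7% |

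The values of S and k are illustrative; the documents give neither. This route taken alone can only raise the rate. Selection on misoprostol timing and route acts alongside it and could move the rate either way.

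**The case against.** The strongest reply is that the plan already covers the point. The all-enrolled analysis is committed to in the next sentence of 9.3, the disposition of participants will be shown in a flow chart, and the secondary aims are hypothesis generating with no testing. For resolution, leading with women who took the regimen as instructed is a defensible choice in a pilot. All of this stands, and it keeps the point modest. It does not settle the AE question, because for AEs the selected set still comes first.

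A reader might infer three stronger things that the documents do not support.

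- **That the lead set is known to be chosen by outcome, or that the lead resolution rate is biased upward.** Withdrawal for an AE is a discretion in 7.2, and no rate is given. UPA is a single observed dose, so after misoprostol mostly follow-up remains. Whether a required Day 8 visit counts toward Day 3/8 is not settled by 9.3 or 9.4.2. Section 7.3 also provides for active contact and rescheduling.
- **That the lead set will be about half the sample.** The 9.1 thresholds are hypotheses to exceed, not forecasts. At 36 adherent and 38 retained the loss of precision is small.
- **That safety oversight is weakened.** Sponsor review of liver tests in the first 20 women (8.2), documentation of all on-study AEs (8.3.4), expedited reporting (8.3.6) and the suspension criteria (10.1.2) do not depend on 9.3. What is affected is the summary tables.

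**Conclusion.** The point holds. Section 9.3 leads AE and resolution reporting with a set defined after exposure, and neither 9.3 nor 9.4.4 supplies an all-treated denominator. It is firmest for side effects and AEs, where exposure is certain for every woman dosed. For resolution it is a lesser matter that rests partly on an unsettled reading of Day 3/8.

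On an assumed 40 women dosed, the upper limit for an unseen AE is 16.1% to 18.5% when both thresholds are only just met, and 9.7% to 10.3% at 36 adherent and 38 retained, against 8.8% for everyone dosed. The net direction of bias is not established. No data are lost, the outcomes are descriptive, and the primary feasibility outcomes are unaffected. It should be corrected because the first-reported figures would otherwise leave out exposed women and the remedy is cheap.

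**What to change.** 1. In 9.3, define a set of all women who received UPA. Section 5.4 already separates those who consent but are not given it.
2. In 9.3 and 9.4.4, make this the lead set and the denominator for every side effect and AE, including those outside the 9.4.3 list.
3. Use the same lead set for all three resolution outcomes in 9.4.3: sac absence on Day 3, additional misoprostol, and uterine aspiration within 30 days. Show missing results as their own category, as 9.4.1 permits ("Where applicable, missing data will be reported as an individual category"), and give a complete-case rate as a check.
4. Move adherent completers to the sensitivity analysis.
5. Report acceptability for all women who answer the Day 30 questionnaire.

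The cost is wording in 9.3 and 9.4.4, one newly defined set and one small extra tabulation. No new data are needed. The new set is not quite the planned all-enrolled set: enrolment precedes dosing (5.5, 7.1), so the two may differ slightly. More than 40 women may be dosed, because 7.2 continues enrolment after withdrawals to reach the target of 40. The lead rates may move in either direction.

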9.4 STATISTICAL ANALYSES

9.4.1 GENERAL APPROACH

Continuous variables will be summarized using mean and standard deviation or median and range depending on the distribution and categorical variables will be described as frequency and percentage. All statistics will be reported with 95% confidence intervals. Where applicable, missing data will be reported as an individual category. As this is a pilot feasibility study with a small sample size, no formal statistical testing will be completed. The principal investigator will be responsible for all data management and data analysis. Statistical calculations will be performed in Stata 15.1.

9.4.2 ANALYSIS OF THE PRIMARY FEASIBILITY OUTCOME VARIABLE(S)

- Recruitment (%): number of participants in study/number of patients screened for participation
- Adherence (%): number of participants adhering to study intervention (UPA + misoprostol vaginally after 6 to 18 hours)/number of participants in study
- Retention (%): number of participants attending all study visits (day 0, 3/8, 30)/number of participants in study

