4 STUDY DESIGN

4.1 OVERALL DESIGN

This is a phase 2 single site pilot study of UPA for use in medical management of early pregnancy loss. Our hypothesis is that UPA will be a feasible option for women desiring medical management. Specifically, we estimate that over 60% of participants screened for participation will enroll in the study (based on a recruitment rate of 75% in a prior study of mifepristone plus misoprostol for EPL) [2]. Additionally, we estimate that greater than 50% of participants will be able to adhere to the study protocol in taking UPA and misoprostol at the designated times and greater than 90% of participants will be able to complete follow up for the study. This is a pilot study with a small sample size and thus our secondary aims will only be for hypothesis generating activities, not hypothesis testing activities.

The study will be conducted at UNC Chapel Hill. Patients will be approached as a convenience sample from patients diagnosed with EPL on viability scan at UNC Chapel Hill OBGYN clinics and UNC Chapel Hill Emergency Department between 5- and 12-weeks' gestation desiring medical management. Participants will be provided counseling regarding their EPL by their OBGYN physician and subsequently screened for eligibility by a research coordinator. Based on prior data on recruitment in this setting and number of patients seen desiring medical management for EPL at UNC Chapel Hill, we anticipate 40 women will be eligible for participation and desire participation in the study after recruitment for 12 months.

After providing informed consent, participants will complete a demographic questionnaire and ensure that they have appropriate baseline lab work (hemoglobin, ABO/Rh status, liver function testing). Participants will all receive the study intervention of 90mg UPA and will be instructed to self-administer 800mcg misoprostol vaginally 6 to 18 hours after the study drug is administered. Self-administration of misoprostol is the standard of care for medical management of EPL. As all participants will receive the same intervention, no randomization or blinding will take place. Participants will receive an

appointment card with their follow up appointment date that also provides space for participants to document their misoprostol timing at home.

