Once early pregnancy loss has been diagnosed on ultrasound, patients are referred back to their primary OBGYN provider for counseling on the diagnosis and discussion of management options, often on the same day as the ultrasound. Patients desiring medical management of EPL are referred to the GYN consultation team at UNC via a telephone call for more information regarding medical management and prescription of the requisite medications. The GYN consultation team will offer patients the standard of care of mifepristone and misoprostol versus admission into the study for ulipristal acetate and misoprostol. Patients interested in the study will then be approached by the research staff. Patients who initially elect for expectant management of their early pregnancy loss but desire medical management at a later date may be offered admission into the study as well within the first two weeks following diagnosis, as over 50% of patients will pass their pregnancy after two weeks following diagnosis [27].

Thus, patients approached for participation will meet the following criteria:

- Diagnosed with early pregnancy loss or anembryonic gestation between 5- and 12-weeks' gestation on viability ultrasound at UNC Chapel Hill OBGYN clinics and UNC Chapel Hill Emergency Department
- Desire medical management of early pregnancy loss and are clinically stable to do so (not hemodynamically unstable or with active vaginal bleeding)
- Interested in learning more about the study from research team

To aid in recruitment efforts, flyers will be placed in each of the two recruitment locations and brochures will be offered to patients if they are considering admission to the study but need time to process their diagnosis. All flyers and brochures will have contact information for the study team so

patients can reach out to the research team directly. Provider flyers will also be placed in the provider workspaces at both recruitment locations and in the GYN workspace at UNC Chapel Hill where the GYN consultation team is based to provide detailed information on the study and eligibility requirements. All study materials will be written to an appropriate reading level to ensure comprehension among all potential participants.

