All counseling on the diagnosis of early pregnancy loss and options for management of early pregnancy loss will take place prior to patient being approached by the research staff. Research staff will reach out to potential participants via telephone call to schedule an eligibility screening at the UNC Same Day Clinic. Research staff will then assess patients for study eligibility and proceed with study activities if the patients are eligible for participation.

Participants will enroll in the study once they are screened for inclusion and exclusion criteria from the study team and the study team has been able to review laboratory tests (hemoglobin, hepatic function tests) to ensure the patient is an appropriate candidate for enrollment. Patients will be offered enrollment into the study and then complete their baseline visit including the demographic questionnaire and administration of UPA.

Spanish-speaking patients make up a key demographic seeking OBGYN care at UNC Chapel Hill, with approximately 10% of individuals identifying as Latinx in the surrounding catchment area. As such, we will include Spanish speaking patients within our study population. All consent and data collection forms will be translated into Spanish for use with this patient population. Additionally, all patient interactions will take place with a Spanish-certified research staff member or with a certified Spanish interpreter (either in person or via telephone).

All women recruited to the study will be pregnant but have already been diagnosed with an early pregnancy loss and thus do not have any risks to an ongoing pregnancy by participating in the study. Participants will be offered psychological support for their loss as part of their standard care for early pregnancy loss. No other vulnerable patients will be included in the patient population including minors under 18 years of age, prisoners, or patients unable to provide informed consent.

UNC-Chapel Hill students and employees may seek OBGYN care at UNC-Chapel Hill and will not be excluded from the study. Any information regarding medical care for UNC-Chapel Hill students or employees will be documented appropriately in their medical charts, which are confidential from UNC-Chapel Hill faculty or employers. Additionally, as with all other patients, all research materials relating to the study will be kept confidential and will not be shared with UNC-Chapel Hill faculty or employers.

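### The recruitment rate begins after the GYN team's offer, so women who decline there enter no planned count; the screening step needs fixing in one place, and one clause of 9.2 is wrong

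*Combined protocol and SAP*

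**What the plan says.** **The outcome.** Sections 3 and 9.4.2 define it alike: "Recruitment (%): number of participants in study/number of patients screened for participation". Section 9.1 sets the expectation: "Recruitment: >60% participants screened for participation enrolled in study". Section 4.1 repeats the 60% and cites 75% from a prior trial. Under 9.4.1 every statistic carries a 95% confidence interval and no formal testing is done.

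**The route in.** Section 5.5 gives the order for women who want medical management: "The GYN consultation team will offer patients the standard of care of mifepristone and misoprostol versus admission into the study". Then: "Patients interested in the study will then be approached by the research staff". The next step is a call: "Research staff will reach out to potential participants via telephone call to schedule an eligibility screening at the UNC Same Day Clinic". There is a second route. Flyers and brochures carry the study's contact details so that "patients can reach out to the research team directly", and "brochures will be offered to patients if they are considering admission to the study but need time to process their diagnosis".

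**What is recorded.** The register in 5.4 covers women screened who prove ineligible or do not consent. Its fields include dates of referral and contact and an outcome that may be a refusal. Section 5.5 bars the study team from obtaining further patient details before referral. The disposition list in 9.3 starts with the number screened.

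**Accrual.** Section 9.2 plans 40 participants in 12 months. It describes two patients per week as net of eligibility and wish to take part, then says about 100 women will be diagnosed in the year and 40 will enroll, citing 300 participants from 800 patients with early pregnancy loss. Section 5.5 gives two per week as all women presenting with a loss at clinic viability scans.

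**The concern.** Section 4.2 says the pilot is meant to show, among other things, that patients are willing to join a study of this kind. At this site the first opportunity to say no comes at the GYN team's offer, against an established alternative. Women who decline there are neither referred nor screened, and no document provides for counting them. The reported rate could therefore look favorable while an unknown number turned the study down one step earlier. A team planning the larger trial needs to know how many women must be offered it to enroll one, and enrolled/screened does not tell them.

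The denominator also has an unclear edge. If a referred woman who refuses at the scheduling call may or may not count as screened, two analysts could report different primary rates from the same records. The planned confidence interval covers sampling error only; it reflects neither women left out of the denominator nor uncertainty about who belongs in it.

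The clause in 9.2 matters less. It misstates which population the weekly figure describes, and a reader could carry the wrong accrual rate into a later trial.

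**Working it through.** **1. Reproduce the target of 40.** Inputs: two per week (5.5, 9.2) and 300 of 800 (5.5, 9.2).
- Diagnosed per year: 2 x 52 = 104, in line with about 100.
- Expected to enroll: 104 x 300/800 = 39; from exactly 100, 37.5. Both are close to 40.
- If the two per week were already eligible and willing, 40 would be reached in 40/2 = 20 weeks, not 12 months.

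So two per week is the diagnosed pool, as 5.5 says. The clause in 9.2 is wrong and the target is not.

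**2. What the 60% implies.** 40/66 = 60.6% and 40/67 = 59.7%, so with 40 enrolled the expectation is met only if at most 66 women count as screened.

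**3. Direction of the gap at the offer.** On the GYN route every woman screened was first offered the study, so screened ≤ offered. The numerator is the same, hence enrolled/screened ≥ enrolled/offered.

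**4. Illustrated size.** The documents give no number of refusals. As a starting assumption take 53 screened, near the cited 75%: 40/53 = 75.5%, exact (Clopper-Pearson) 95% CI 61.7% to 86.2%. Assume all 53 came by the GYN route and everyone who did not decline was screened.

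| Declined at offer (assumed) | Enrolled/offered |
|---|---|
| 0 | 40/53 = 75.5% |
| 5 | 40/58 = 69.0% |
| 10 | 40/63 = 63.5% |
| 14 | 40/67 = 59.7% |

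The last value lies below the whole interval for enrolled/screened. The two are different quantities, so this shows only that the interval does not speak to uptake at the offer.

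**5. Where screening sits.**
- 1.3, Visit 1 in 4.1, and the Same Day Clinic appointment in 5.5 place it at Visit 1, Day 0. On that reading a refusal at the call is not counted.
- The 5.4 register is for women screened, yet it records referral, contact and refusal. On that reading the same woman may be counted.
- 8.2 dates the coordinator's chart review to diagnosis, with the eligibility questionnaire following. This sits badly with the 5.5 rule on information before referral.

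With 53 seen at clinic and 5 or 10 refusals by telephone (assumed), the primary rate is 75.5% if they are left out, and 40/58 = 69.0% or 40/63 = 63.5% if they are included.

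**6. Why the routes must be kept apart.** Suppose 10 of the 53 contacted the team directly with no prior GYN offer, all 10 enrolled, and 14 declined at the GYN offer. Women offered by the GYN team: 43 + 14 = 57. Dividing all enrolled by these gives 40/57 = 70.2%; the GYN route alone gives 30/57 = 52.6%.

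**The case against.** Enrolled/screened is a usual pilot measure, is defined identically in 3 and 9.4.2, and drives no test or stop/go rule. Most sections place screening at Visit 1. No sentence says refusals at the offer are excluded; their absence is inferred from the sequence in 5.5 and the scope of 5.4 and 9.3. All of this stands. It limits the severity, but it does not supply the missing count or settle the conflict with the register.

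Several stronger readings are tempting and are not supported:

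- *The rate overstates willingness whenever anyone declines at the offer.* Enrolled/screened also falls through ineligibility found after approach, for example on the laboratory tests. With assumed numbers, 60 offered, 6 declining, 54 screened and 14 ineligible leave 40 enrolled. Enrolled/screened is 40/54 = 74%, while 54/60 = 90% did not decline at the offer. Enrolled/offered, at 40/60 = 67%, is no purer a measure of willingness. It measures yield per offer.
- *Women have already chosen the study when research staff meet them.* Under 5.5 they have shown interest in hearing more. Consent comes later, and 5.4 provides for recording refusals after screening.
- *The true recruitment rate will be 40%.* This divides 40 by the roughly 100 diagnosed, or by the roughly 100 approached that 10.1.7 implies when it treats 10 as about 10%. The plan's outcome has a different denominator.
- *The cited 75% conflicts with 300/800 from the same reference.* Both can be true at different stages, and the documents alone do not show an error.

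**Conclusion.** The point holds in a limited form. The plan has no count of women who decline at the GYN offer. On that route the primary rate cannot be lower than uptake among women offered the study, and may be higher by an amount the data as planned cannot show. The rate can be reported as it is, but cannot alone project accrual for a larger trial. The counting step needs one definition, because the 5.4 register and the timing in 8.2 do not fit the Visit 1 reading found elsewhere. The clause in 9.2 is a wording error with no effect on the target.

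The sizes above are illustrations: they assume 53 screened and chosen numbers of refusals. The direction of the gap needs no assumption beyond the order of steps in 5.5. The harm is to interpretation and planning, so the severity is minor to should-fix.

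**What to change.** (a) Keep enrolled/screened as the primary rate. Ask the GYN team to keep a tally without identifiers, marked at each woman's first offer only: offered, referred, declined, undecided. In the 9.3 flow chart report offered, declined at offer, referred, screened, ineligible, declined after screening, and enrolled. Give enrolled/offered for the GYN route beside the primary rate, with no 60% threshold attached. Show women who contact the research team directly as a separate route, and ask whether the GYN team had already offered them the study; if so, they belong to the GYN route.

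(b) In 3, 9.1 and 9.4.2 tie screening to one step consistent with the 5.4 register, and align the timing in 8.2. Entry on the register is one option, since it already has a field for refusals.

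(c) In 9.2 delete the clause saying that the two per week are already net of eligibility and wish to take part. Optionally add that more than 60% with 40 enrolled means at most 66 screened.

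The cost is short wording changes and a tick sheet. The tally is a small burden on clinical staff outside the research team, and missed entries would make enrolled/offered too high. Counting from the register may lower the primary rate. Offers not tallied when made may not be recoverable later.
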